8.2 Safety Reporting Process – principal investigator responsibilities

The principal investigator shall report all adverse events and device deficiencies in the appropriate sections of the e-CRF and provide where requested by the sponsor, the necessary clinical or technical information that may contribute to clarifying the circumstances.

The principal investigator shall report all serious adverse events (SAEs) and device deficiencies (DDs) that might have led to a SAE: if a) suitable action had not been taken or b) intervention had not been made or c) if circumstances had been less fortunate, to the sponsor within 24 hours after knowledge of the event using the appropriate e-CRF.

When required by national or local regulations, the principal investigator shall also notify the EC/IRB and Regulatory Agencies of all reportable events according to national regulations within the by regulations required timelines and may also be requested by the EC/IRBs to provide annual reports. The principal investigator shall document all adverse events and device deficiencies in the e-CRF from the point of enrollment until the subject is exited from the study.

8.3 Information provided by the clinical investigation site

The principal investigator will provide the following information, at a minimum, for each adverse event (AE) or Adverse Device Effect (ADE):

- Date of the AE or ADE.
- Date Principal Investigator (or authorized designee) became aware of AE or ADE
- Description of AE or ADE, relevant diagnostic findings
- Treatment
- Resolution
- Assessment of:
- 1. severity of the event
 - a. Mild: asymptomatic or mild symptoms; clinical or diagnostic observations only; intervention not indicated.
 - b. Moderate: minimal, local or noninvasive intervention indicated; limiting
 - c. Severe: medically significant but not immediately life-threatening; hospitalization or prolongation of hospitalization indicated; disabling
 - i. Life-threatening: urgent intervention indicated, disabling
 - ii. Fatal: death related to AE

- 2. relationship of the event to the investigational device (related, unlikely related, possible related, probable related or causal relationship)
- 3. relationship of the event to the index procedure (related, unlikely related, possible related, probable related or causal relationship)
- 4. causality
 - a. disease under study
 - b. lack of performance of the investigational device or comparator/worsening of treated condition
 - c. medical history
 - d. concomitant or previous medication
 - e. other (specify)

The principal investigator will supply the sponsor and/or designee, with any additional information related to the safety reporting of a particular event upon request.

The sponsor is responsible for the classification of all adverse events and ongoing safety evaluation of the clinical investigation and shall:

- 1. Review the investigator's assessment of all adverse events and determine and document in writing their seriousness, severity and relationship to the investigational device; in case of disagreement between the sponsor and the principal investigator(s), the sponsor shall communicate both opinions to concerned parties.
- 2. Review all device deficiencies and determine and document in writing whether they could have led to a serious adverse device effect; in case of disagreement between the sponsor and the principal investigator(s), the sponsor shall communicate both opinions to concerned parties.
- 3. Ensure the reporting to the Ethics Committee (EC) by the principal investigator(s), of all serious adverse events and device deficiencies that could have led to a serious adverse device effect, if required by national regulations or by the EC.
- Review and report all reportable events (including device deficiencies) according to national regulations in acceptable timely conditions and shall monitor for increased incidence and severity.
- 5. Ensure that the EC or other applicable regulatory authorities are informed of significant new information about the clinical investigation, and
- 6. In case of serious adverse device effects and device deficiencies that could have led to serious adverse device effects, determine whether corrective or preventive action is required.

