6.3 Exploratory Endpoints

Any comparisons across timepoints (baseline to 6 months) not described in the primary or secondary endpoints, including but not limited to:

- Demographics
- Medical History
- History of joint osteoarthritis
- Rescue Medication Use
- Treatment Failure
- Injection procedure
- Concomitant medications
- Non-drug therapy.

6.4 Safety Endpoint:

The incidence, severity, and relationship to treatment of all Adverse Events (AE) will be collected from the treatment injection to the 6-month assessment.

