8. SAFETY PROCESSES

Safety of the subjects participating in this clinical investigation will be monitored throughout the clinical investigation using the Adverse Event (AE) reporting process in the EDC system, to identify real and potential safety issues.

Adverse events will be reported according to the ISO 14155:2011, while recognizing and following the requirements including reporting timelines specified in other specific laws, regulations, directives, standards and/or guidelines as appropriate and as required by the countries in which the study is conducted.

All AEs that occur during or after injection will be recorded. Worsening of a condition that existed prior to the study injection should be recorded as an AE. At each assessment during the trial, AEs that have occurred since the previous assessment must be recorded. All subjects will be questioned and evaluated for AEs or complications associated with the procedure. Complications of the injection include, but are not necessarily limited to: pain, swelling, erythema, bleeding and/or infection at the injection site. The Investigator will determine the severity and relationship of each event, as defined above.

AEs observed during the course of this study, regardless of severity or relationship to the device and/or the procedure will be recorded on the CRF. Each reported complication/AE will also include the duration, action taken to address the AE, and the resolution status (e.g. ongoing, resolved). These subjects will continue to be evaluated for safety at all scheduled follow-up points.

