8.1 Definition of Adverse Events

Adverse Device Effect (ADE)

Adverse event related to the use of an investigational medical device.

Note 1: This definition includes adverse events resulting from insufficient or inadequate instructions for use, deployment, implantation, installation, operation, or any malfunction of the investigational medical device.

Note 2: This definition includes any event resulting from the use error or intentional misuse of the investigational medical device.

Adverse Event (AE)

Any untoward medical occurrence, unintended disease or injury or untoward clinical signs (including an abnormal laboratory finding) in subjects, users or other persons whether or not related to the investigational medical device.

Note 1: This includes events related to the investigational medical device or the comparator.

Note 2: This includes events related to the procedures involved.

Note 3: For users or other persons this is restricted to events related to the investigational medical device.

Device Deficiencies (DD)

The inadequacy of a medical device with respect to its identity, quality, durability, reliability, safety or performance.

Note: Device deficiencies include malfunctions, use errors, and inadequate labeling.

Device deficiencies that did not lead to an adverse event but could have led to a medical occurrence

- a) if either suitable action had not been taken,
- b) if intervention had not been made, or
- c) if circumstances had been less fortunate,

shall be reported under the same conditions as a serious adverse event.

Malfunction

Failure of an investigational medical device to perform in accordance with its intended purpose when used in accordance with the instructions for use or Clinical Investigation Plan.

Serious Adverse Events (SAE)

An adverse event that:

- a) led to a death,
- b) led to a serious deterioration in the health of the subject user or other persons that either resulted in:
 - 1) a life-threatening illness or injury, or
 - 2) a permanent impairment of a body structure or a body function, or
 - 3) in-patient or prolonged hospitalization. or
 - 4) medical or surgical intervention to prevent life threatening illness or injury or permanent impairment to a body structure or a body function.
- c) led to foetal distress, foetal death or a congenital abnormality or birth defect

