9.2.2 Adverse Events

Subjects with AEs will be summarized with frequencies and percentages by system organ class and preferred term, severity, and relationship to investigational product/procedure. In summaries of AEs by severity and relationship to investigational product/procedure, subjects reporting multiple episodes will be counted once under the worst severity and the strongest relationship, respectively. Serious Adverse Events will also be presented by relationship to investigational product/procedure.

Adverse events occurring prior to the index treatment will not be recorded in this trial.

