4.4 ADVERSE EVENTS

All AEs will be coded according to MedDRA. Safety assessments will include Treatment-Emergent Adverse Events (TEAEs) which are defined as AEs with an Investigator assessment of definitely, probably, or possibly related to CTM. TEAEs will be summarized with frequencies and percentages by system organ class and preferred term, severity, and relationship to study CTM for each treatment group. In summaries of TEAEs by severity and relationship to CTM for subjects reporting multiple episodes, all reported events will be included, not only the worst reported case. Serious Adverse Events will also be presented by relationship to the CTM.

The number of subjects with at least one AE will be tabulated for each treatment group. Differences between the treatment groups will be tested using Fisher's exact test. Then the number of AEs for each treatment group will also be tabulated.

The number of subjects and the number of AEs will be tabulated by severity, relationship, and local injection site specific events versus non local events.

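### Protocol 8.3's adverse-event relationship scale has no level for unrelated events, leaves one level unranked, and does not match the SAP's related-event rule

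*Protocol*

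**What the plan says.** Protocol 8.3, items 2 and 3 of the assessment list, sets two relationship grades for every adverse event. The first is the "relationship of the event to the investigational device (related, unlikely related, possible related, probable related or causal relationship"; the second is the "relationship of the event to the index procedure (related, unlikely related, possible related, probable related or causal relationship". The five levels are identical. Neither item defines them or gives an order. Protocol section 8 says relationship is determined by a definition given above, but none precedes it in that section.

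Unrelated events must be captured. Section 8 states that adverse events "regardless of severity or relationship to the device and/or the procedure will be recorded on the CRF", and the definition in 8.1 covers occurrences "whether or not related to the investigational medical device".

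Relationship is a named component of the safety endpoint in Protocol 6.4: "The incidence, severity, and relationship to treatment of all Adverse Events (AE) will be collected". For tabulation, Protocol 9.2.2 says that "subjects reporting multiple episodes will be counted once under the worst severity and the strongest relationship, respectively", and it refers to relationship to the product or procedure.

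SAP 4.4 uses other terms. The events it summarises are "defined as AEs with an Investigator assessment of definitely, probably, or possibly related to CTM". For subjects with several episodes it includes every reported event rather than only the worst.

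**The concern.** A site that follows 8.3 literally has nowhere to put an event it judges unrelated. Such events are foreseeable: Protocol 4.2 lists headache and back pain among events not related to the knee in the earlier Cingal knee work. The site must either grade the event *unlikely related* or use *related*. That level stands first, before *unlikely*, in a list that otherwise rises in strength, which is where *not related* would be expected. Up to 10 sites may not all read it the same way.

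The analyst then has to apply an SAP rule that names a level nobody is asked to record and does not say where *related* or *causal relationship* belongs. What is at stake is the relationship component of the safety endpoint, in a single-arm study where related-event incidence has no control group to set it against.

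The SAP's use of relatedness to define treatment-emergent events is a separate matter, and nothing here depends on it.

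**Working it through.** The plan gives no figure to reproduce. The check is a comparison of the two sets of levels, followed by simple arithmetic.

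**Step 1: map the levels (Protocol 8.3 against SAP 4.4).**

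| Protocol 8.3 level | SAP 4.4 counterpart | In the SAP's related set? |
|---|---|---|
| related | none named | undefined |
| unlikely related | none named | no |
| possible related | possibly | yes |
| probable related | probably | yes |
| causal relationship | none named; *definitely* is the natural match | presumably yes, not stated |
| not collected | definitely | yes |

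Two of the five protocol levels match by name, one falls outside the set, and two have no named counterpart. One of the three SAP levels is not collected. The number of levels valid for an unrelated event is 0 of 5 on each of the two scales.

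**Step 2: the two readings of *related*.**

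- *A slip for* not related. The scale is then complete and ordered, with *causal relationship* alone at the top. The error to fear is that an analyst pools *related* with *causal relationship* as *definitely*, so that unrelated events enter the related set.
- *Meant literally.* There are then two positive levels with no order between them and still no level for unrelated events. The error to fear is that *related* is left out because it is not among the SAP's three names, so that related events are lost.

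If sites differ in their reading, no single mapping is right for all the data.

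**Step 3: size.** Related-event incidence is x/n, where x is the number of subjects with at least one event in the related set. Protocol 6.5 gives n as up to 25, and 9.1 as at least 25; take n = 25.

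- One subject misclassified: 1/25 = 4 percentage points.
- k subjects: k × 4 points. For illustration only, k = 3 gives 3/25 = 12 points.

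A subject moves only if no other event already places that subject in the set. The documents give no basis for predicting k.

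**Step 4: what merging unrelated events with *unlikely* does.** Both lie outside the SAP's three levels, so the related-event count does not change. What is lost is the distinction in the tables that break adverse events down by relationship (Protocol 9.2.2 and the last paragraph of SAP 4.4).

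**Step 5: object and counting rule.** Protocol 8.3 records two grades per event, device and procedure. SAP 4.4 uses one object, CTM, and does not say which grade feeds it. Protocol 9.2.2 counts a subject once under the strongest relationship; SAP 4.4 includes all events. Ordering the scale makes the first rule computable but does not settle which rule applies.

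**The case against.** The best reply is that this is one wording slip. If *related* is read as *not related*, the missing level, the second positive level and the unranked top all disappear together, and *causal relationship* differs from *definitely* only in label. That is probably right about the origin, and it argues against counting several independent failures. It does not remove the error: the printed word states the opposite of what was probably meant, and it is printed twice.

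Safeguards also exist. Item 4 of the same list records alternative causes, the sponsor must make its own written determination of relationship to the device, and Protocol 10.2 requires unclear data to be queried. These reduce the risk. But item 4 is not a relationship grade, the sponsor's relationship review names only the device and is given no other scale, and SAP 4.4 analyses the investigator's assessment.

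Three stronger readings are tempting and not supported:

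- *That relationship cannot be recorded or tabulated at all.* The possible and probable levels map directly, and incidence and severity do not depend on the scale.
- *That the collected data are wrong.* The eCRF is not among the documents. SAP 1.0 says the SAP is based on the case report forms, and the actual pick-list may be correct.
- *That serious-event reporting fails.* Protocol 8.2 sends all serious events to the sponsor within 24 hours, whatever their relationship.

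**Conclusion.** The protocol text is wrong as written and should be corrected. An unrelated event has no valid grade. Membership of the SAP's related set is undefined for *related* and only inferable for *causal relationship*. Two graded objects become one without a stated rule.

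The consequence is confined to the relationship component of the safety endpoint: 4 percentage points of related-event incidence for each subject misclassified, in either direction. The more credible direction is *related* meant as *not related* and then counted as related.

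This rests on 25 treated subjects and on sites and analysts working from the protocol and SAP as printed. If the eCRF already carries a correct list, the data may be sound, and what remains is to bring both documents into line with it.

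**What to change.** 1. In Protocol 8.3, items 2 and 3, replace *related* with *not related*. This gives one ordered scale: not related, unlikely, possible, probable, causal relationship. State that strongest relationship in 9.2.2 follows this order.
2. In SAP 4.4, replace *definitely* with *causal relationship*. Tabulate relationship to device and to procedure separately, and state which grade or grades define the related-event set.
3. Reconcile the counting rules in Protocol 9.2.2 (once per subject) and SAP 4.4 (all events). If both subject counts and event counts are wanted, say so and label each table.
4. Check the eCRF pick-list against the corrected scale, and query any event already coded *related*.

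The cost is a wording change in the protocol, a short revision of one SAP section, an eCRF check with a pick-list change only if one is needed, and queries limited to events coded *related*. There is no added burden for subjects.

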9. STATISTICAL CONSIDERATIONS

9.1 Sample Size

The primary analysis will be the mean change in index ankle pain from baseline to 6 months as measured by the Numerical Rating Scale.

The hypothesis to be tested is:

 H_0 : $\mu_{DMON} = 0$ versus H_A : $\mu_{DMON} > 0$.

In this hypothesis, μ_{DMON} is the mean change in pain from baseline at 6 Months in CINGAL treated patients.

The data will be analyzed via a one sample t-test.

It is assumed that a mean change in pain from baseline of 2 points represents a clinically significant improvement with a standard deviation of 2 - 2.5 points, for 80% power and alpha of 5% then a total of 15 subjects are required. To ensure sufficient subjects are available at the 6 month follow up, it is proposed to enroll and treat at least 25 subjects which should be more than adequate to demonstrate that treatment of the study population with CINGAL would reduce joint pain at 6 months.

Single sites should not enroll and treat more than 50% of the total enrollment.

9.2 Statistical Methods

Tabulation of summary statistics, graphical presentations, and statistical analyses will be performed. Where not otherwise specified, the last pre-treatment observation will be used as baseline for calculating post-treatment changes from baseline. The primary presentations and analyses will be based on data pooled across study centers. All testing and confidence intervals will use a significance level of 5%.

9.2.1 Demographic and Baseline Characteristics

All demographic and baseline characteristics will be tabulated by treatment group. Medical history findings, physical examinations and concomitant medications will be tabulated.

9.2.2 Adverse Events

Subjects with AEs will be summarized with frequencies and percentages by system organ class and preferred term, severity, and relationship to investigational product/procedure. In summaries of AEs by severity and relationship to investigational product/procedure, subjects reporting multiple episodes will be counted once under the worst severity and the strongest relationship, respectively. Serious Adverse Events will also be presented by relationship to investigational product/procedure.

Adverse events occurring prior to the index treatment will not be recorded in this trial.

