- Subject has significant varus or valgus deformity greater than 10 degrees in either knee.
- 16. Subject requires consistent use of an assistive device (e.g. wheelchair, walker, etc.) Occasional use of a cane is acceptable.
- 17. Uncontrolled diabetes with HbA1c of >7%.
- 18. Subject is a woman who is pregnant or breastfeeding at the Screening Visit or a woman of child bearing potential who refuses to use effective contraception during the course of the study.
- 19. Subject is receiving or in litigation for worker's compensation.
- 20. Otherwise determined by the investigator to be medically unsuitable for participation in this study.

Baseline Inclusion Criteria

1. NRS pain on walking ≥4 and ≤ 9 in index ankle

Baseline Exclusion Criteria

- Subject has a decrease of ≥ 2 in the NRS pain on walking from Screening to Baseline in the index ankle.
- 2. Subject has a contraindication to continue with the study treatment injection based on the visual appearance of the synovial fluid aspirate.

Criteria for Evaluation

Primary Endpoint:

 Reduction of index ankle Numerical Rating Scale (NRS) pain on walking from baseline to 6 Months post injection.

Secondary Endpoints:

- Improvement in AOFAS index from baseline to 6 months post injection.
- Improvement in Patient Global Assessment (PGA) from baseline to 6 months post injection.
- OMERACT-OARSI responder rate in the index ankle at 6 months post injection.
- Time to treatment failure
- Reduction in Medication usage from baseline to 6 months post injection.

Exploratory Endpoints

Any comparisons across timepoints (baseline to 6 months) not described in the primary or secondary endpoints including but not limited to:

Demographics

	Medical History				
	History of joint osteoarthritis				
	Rescue Medication Use				
	Treatment Failure				
	 Injection procedure Concomitant medications 				
	Non-drug therapy				
	2				
	Safety Endpoint:				
	The incidence, severity, and relationship to treatment of all Adverse Events (AE) will be collected from the first treatment injection to the 6 month assessment.				
Statistical Analysis	The primary analysis on the endpoints will be performed on the ITT (Intent to Treat) populations. All Primary and Secondary endpoints will be analyzed using the ITT population.				

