7. STUDY PROCEDURES

7.1 Schedule of Events

Assessments	Screening Visit	Baseline Visit	Month 1 Visit	Month 3 Visit	Month 6 Visit
Assessments	Day -14 to -7 ±2 days	Day 0	±3 days	± 7 days	± 7 days
Informed Consent	Х				
Evaluation of Enrollment Criteria	х	х			
Demographics	Х				
Vital Signs	Х				
History Joint OA (Index & Contralateral for hip, knee and ankle)	х				
Medical History	Х				
Concomitant Medication	х	Х	X	Х	х
Assess non-drug therapies	Х	Х	X	Х	х
Adverse Event Assessment		Х	X	Х	х
Collect & Review Subject Diary		Х	Х	Х	х
Rescue Medication usage / washout		Х	Х	Х	х
Patient Global Assessment (PGA)	х	Х	Х	Х	х
AOFAS index for index and contralateral ankle	х	х	Х	х	Х
Index and Contralateral Joints Pain (0-10 Numeric Rating Scale) for Hip, Knee and Ankle joints	х	х	Х	х	х
Physical Evaluation of Index and Contralateral Joints for Hip, Knee and Ankle joints	х	х	Х	х	х
Study Injection		Х			
Dispense Subject Diary	x	х	X	X	

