3.0 Objectives

The goal of these studies is to demonstrate the clinical improvement and safety in patients treated with CINGAL for hip osteoarthritis, shoulder osteoarthritis, and ankle osteoarthritis. Specifically, this study will provide confirmation to the effectiveness and safety of CINGAL at relieving the specified joint pain to 6 months post-treatment.

PRIMARY ENDPOINT:

• Reduction of index joint Numerical Rating Scale (NRS) pain on walking from baseline to 6 Months post injection (CINGAL 20-01), joint pain from baseline to 6 Months post injection (CINGAL 20-02), and pain on walking from baseline to 6 Months post injection (CINGAL 20-01).

SECONDARY ENDPOINTS:

- Improvement in Lequesne Hip index joint from baseline to 6 months post injection. (CINGAL 20-01 only)
- Improvement in DASH score for index joint from baseline to 6 months post injection (CINGAL 20-02 only)

- Improvement in AOFAS index joint from baseline to 6 months post injection (CINGAL 20-03 only).
- Improvement in Patient Global Assessment (PGA) from baseline to 6 months post injection.
- OMERACT-OARSI responder rate in the index joint at 6 months post injection.
- Time to treatment failure
- Reduction in Medication usage from baseline to 6 months post injection.

EXPLORATORY ENDPOINTS

Any comparisons across timepoints (baseline to 6 months) not described in the primary or secondary endpoints, including but not limited to:

- Demographics
- Medical History
- History of joint osteoarthritis
- Rescue Medication Use
- Treatment Failure
- Injection procedure
- Concomitant medications
- Non-drug therapy

SAFETY ENDPOINT:

The incidence, severity, and relationship to treatment of all Adverse Events (AE) will be collected from the treatment injection to the 6 month assessment.

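### Protocol 8.2 and 9.2.2 give different starts for adverse event recording, and the planned AE tables omit some procedure-related and unrelated events (minor)

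*Protocol*

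**What the plan says.** **Start of recording.** Protocol 8.2 requires the principal investigator to "document all adverse events and device deficiencies in the e-CRF from the point of enrollment until the subject is exited from the study". Protocol 9.2.2 states the opposite for the time before dosing: "Adverse events occurring prior to the index treatment will not be recorded in this trial". Four other places begin at the injection:

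- Synopsis, safety endpoint: "collected from the first treatment injection to the 6 month assessment".
- Protocol 6.4: "will be collected from the treatment injection to the 6-month assessment".
- SAP 3.0: "will be collected from the treatment injection to the 6 month assessment".
- Protocol 8: "All AEs that occur during or after injection will be recorded". The same paragraph adds that at each assessment "AEs that have occurred since the previous assessment must be recorded".

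The 7.1 schedule marks the row "Adverse Event Assessment" at Baseline and at each follow-up visit, but not at Screening.

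**Who is analysed.** The synopsis limits safety analyses to subjects treated with Cingal in the ankle. Protocol 9.2.3 and SAP 4.5 refer to subjects who undergo Study Treatment, a term that neither document defines.

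**What is tabulated.** Protocol 9.2.2 plans tables of subjects with AEs by organ class and preferred term, by severity, and by relationship to product or procedure. SAP 4.4 defines treatment-emergent events as those judged at least possibly related to CTM, and builds its organ class and preferred term tables on those alone.

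**The concern.** Both start rules govern what goes into the database, so they cannot be reconciled as a wide recording window with a narrower analysis window. A site that follows 8.2 may enter an event that arises after consent and before dosing, while a site that follows 9.2.2 leaves it out. Up to 10 sites are planned, so the record could differ by site for reasons unrelated to the subjects. The interval is not inert: subjects stop all analgesics except paracetamol at least seven days before the injection, and paracetamol for the last 48 hours before Baseline.

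The two reporting gaps matter because the study's stated goal includes safety, and protocol 4.2 names harms of the injection procedure itself. An event in a subject who had the needle but no Cingal has no planned table. In a dosed subject, an event attributed to the procedure but not to CTM drops out of the organ class and preferred term tables if the SAP is followed.

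**Working it through.** The plan gives no figure to reproduce here. The check compares the text, with one bound on the interval.

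**1. Where does enrollment fall?**

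- Protocol 7.3.1 puts consent before enrollment and names enrollment and study treatment as separate steps. Protocol 6.5 likewise speaks of subjects being enrolled and treated. This points to a time before dosing.
- Protocol 6.6, headed Enrollment Criteria, includes the Baseline criteria, the last of which is the look of the aspirate. The 7.1 schedule evaluates enrollment criteria at both Screening and Baseline. This points to Day 0.

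Neither reading is ruled out.

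**2. Bound on the disputed interval.** Inputs: 25 planned subjects (synopsis, 9.1), and 7 to 14 days from Screening to Baseline (7.4).

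- Enrollment near Screening: 25 × 7 = 175 to 25 × 14 = 350 subject-days.
- Enrollment completed on Day 0: about 25 × 0 = 0 subject-days.

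The range is therefore about 0 to 14 days per subject, or 0 to 350 subject-days in all. The screening window is stated slightly differently in 7.1 (with ±2 days) and in the 7.3 heading, so the upper end is approximate. No event rate is given, so the bound cannot be turned into a number of events.

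**3. Does the Baseline AE mark already cover the screening interval?** The list in 7.4 of activities before injection has no AE item. The only AE evaluation described in 7.4 comes after treatment, before the subject leaves the clinic, and that alone explains the mark in 7.1. The look-back sentence in section 8 follows the sentence that limits recording to the injection and later, and may be governed by it. A check before injection is therefore not secured.

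**4. The undosed subject.** The order in 7.4 is local anaesthetic (optional), needle, contrast or air if guidance is used, optional aspiration, the aspirate exclusion check, then 2 ml of Cingal. Baseline exclusion 2 in 6.6.4 can therefore stop a subject after needle entry. Protocol 9.2.3 and SAP 4.5 are ambiguous about that subject, but the synopsis, which requires treatment with Cingal, puts the subject outside the safety set. No other table or listing is planned.

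**5. SAP 4.4 against protocol 9.2.2.**

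| Event in a dosed subject | Organ class and preferred term tables, protocol 9.2.2 | Same tables, SAP 4.4 |
|---|---|---|
| Related to CTM | included | included |
| Related to the procedure, not to CTM | included | left out |
| Unrelated to either | included | left out |

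The SAP still counts all AEs in its overall totals. Its last paragraph tabulates by relationship without saying to what. Protocol 8.3 collects relationship to device and to procedure separately, so the data for the protocol's tables will exist.

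**The case against.** The case for leaving the plan alone is that five of the six places that state a start agree on the injection, so 8.2 is the outlier and its intent can be inferred. If enrollment is complete only when the last Day 0 criterion is met, 8.2 and 9.2.2 nearly coincide. Aspiration is optional, so there may be no undosed subject at all. Serious events must reach the sponsor within 24 hours under 8.2, so mainly non-serious events are exposed.

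Most of this is right and keeps the point minor. It does not remove it. The documents do not define enrollment as Day 0, and 8.2 is the section that instructs the investigator. The SAP 4.4 difference depends on neither reading.

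Three stronger inferences are tempting, and the documents do not support them:

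- *One to two weeks of AE data are lost for every subject.* That is only the upper end of a range that starts near zero.
- *Reactions to the anaesthetic, needle or contrast on Day 0 go unrecorded in dosed subjects.* Section 8 asks about complications of the procedure, 8.1 counts procedure events as AEs, 8.3 asks for relationship to the index procedure, and 9.2.2 itself tabulates it. Reading 9.2.2 to exclude these events would defeat its own table.
- *The medication form shows that AEs must be recorded from consent.* Protocol 7.3.9.3 does ask whether each medication was taken for an AE, but it turns new indications into AEs only after study treatment.

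**Conclusion.** The inconsistency is real and minor. Protocol 8.2 and 9.2.2 give different recording starts. The disputed interval is about 0 to 14 days per subject, depending on where enrollment falls, and the number of affected events is unknown and may be zero. The upper end assumes enrollment at or near Screening and the 7.4 interval.

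The undosed-subject gap rests on the synopsis wording and arises only if a site aspirates and then stops. The documents give no basis for a count. A reader might infer that the Safety Population is wrongly defined, but restricting it to treated subjects is a reasonable choice. What is missing is a place to show the others.

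The SAP 4.4 restriction follows directly from the text and applies to dosed subjects. The primary result is unaffected by any of the three.

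**What to change.** 1. **One recording start.** Preferably ICF signature, with AE tables counting events from the start of the Day 0 injection procedure and earlier AEs listed only. Delete the 9.2.2 sentence; align 8.2, the synopsis, 6.4, section 8 and SAP 3.0; and add an AE check to the pre-injection list in 7.4. At minimum, align 8.2 and 9.2.2 to the start of the injection procedure.
2. **SAP 4.4.** Tabulate all AEs by organ class and preferred term, and by relationship to procedure as well as to CTM, as protocol 9.2.2 states.
3. **One listing** of subjects whose procedure was started but who were not given Cingal, with any AEs. Leave the Safety Population unchanged.

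The cost is wording, one listing that may be empty, and one added question at an existing visit. Sites would record some additional AEs before dosing. The SAP also serves the hip and shoulder studies, so its edits need checking against those protocols. The CRFs are not among the documents, so whether a field must be added for undosed subjects is not known.
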